8.2 SECONDARY EFFICACY ENDPOINTS AND ANALYSES

Part A

SGRQ:

1006696
Parion Sciences Incorporated
CLEAN-PCD
SAP Version 1.0

The SGRQ will have three domains (Symptoms, Activity, Impacts) and Total for age groups ≥ 16 [REDACTED]

SGRQ total score for [REDACTED] will be analyzed using similar analyses as described in [Section 8.1 Part A](#) including mixed effect model and waterfall plot. Note that the mixed effect model will use study baseline for ppFEV1 as a baseline covariate. [REDACTED]

The summary statistics for the actual values and absolute changes from study baseline will be obtained for SGRQ total score [REDACTED].

QOL-PCD:

The QOL-PCD [REDACTED] - adult version, [REDACTED]

[REDACTED]
[REDACTED]
[REDACTED]
[REDACTED] Subjects aged 18 years and older at Day 1 of Part A will complete the Adult version of the questionnaire themselves at all visits. [REDACTED]

The Lower Respiratory Symptoms domain focuses on lung symptoms and the treatments evaluated in this study are targeted toward the lungs.

QOL-PCD Lower Respiratory Symptoms domain for each QOL-PCD questionnaire version will be analyzed using similar analyses for mixed effect model and waterfall plot as described in [Section 8.1 Part A](#). Note that the mixed effect model will use study baseline for ppFEV1 as a baseline covariate. [REDACTED]

1006696
Parion Sciences Incorporated
CLEAN-PCD
SAP Version 1.0

The summary statistics for the actual values and absolute changes from study baseline will be obtained for Lower Respiratory Symptoms domain for [REDACTED] QOL-PCD questionnaire [REDACTED].

Part B

For the Part B secondary efficacy endpoint, the analysis will be based on change from study baseline as well as change from Part B baseline.

SGRQ:

[figure not shown]
SGRQ total score [REDACTED] will be analyzed using ANCOVA model and waterfall plot as described in [Section 8.1 Part B](#).

The summary statistics for the actual values and absolute changes from study baseline and changes from Part B baseline will be obtained for SGRQ total score [REDACTED].

[figure not shown]
[figure not shown]
QOL-PCD:

QOL-PCD Lower Respiratory Symptoms domain for [REDACTED] QOL-PCD questionnaire [REDACTED] will be analyzed using ANCOVA model and waterfall plot as described in [Section 8.1 Part B](#).

[figure not shown]
The summary statistics for the actual values and absolute changes from study baseline and from Part B baseline will be obtained for Lower Respiratory Symptoms domain for [REDACTED] QOL-PCD questionnaire [REDACTED].

1006696
Parion Sciences Incorporated
CLEAN-PCD
SAP Version 1.0

1006696
 Parion Sciences Incorporated
 CLEAN-PCD
 SAP Version 1.0

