### **11.5.2 QOL-PCD**

The QOL-PCD will be completed before the start of any other assessments, including the SGRQ, as noted in [Table 3-2](#) and [Table 3-3](#).

Subjects aged 12 at Day 1 will complete the QOL-PCD-Child version themselves and their parents/caregivers will complete the QOL-PCD-Parent version on all visits, regardless of whether subjects subsequently become 13 years of age during the study. Subjects aged 13 to 17 years at Day 1 will complete the Adolescent version of the questionnaire themselves at all visits. Subjects aged 18 years and older at Day 1 will complete the Adult version of the questionnaire themselves at all visits. The questionnaires provide information about demographics; general quality of life, school, work, or daily activities; and symptom difficulties (pertaining to PCD). Copies of the QOL-PCD used in this study will be provided in the Study Reference Manual. Translations of the QOL-PCD, if available, will be provided for participating centers in non-English-speaking countries.

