3.6 TREATMENT ASSIGNMENT & BLINDING

[figure not shown]
Approximately 150 subjects will be randomized to 1 of 4 treatment sequences in double-blind fashion when they are determined to have met all eligibility criteria. Subjects will be randomized in a 2:2:1:1 ratio, in Part A to one of the 4 treatment sequences, (Treatment Sequence 1 or Treatment Sequence 2; Treatment Sequence 3 or Treatment Sequence 4), stratifying for ppFEV1 severity (<70 or ≥70). Randomization must only occur after all inclusion and exclusion criteria are met and before the first dose of inhaled study drug is administered in Part A on Day 1.

An interactive web or voice response system (IXRS) will be used to assign subjects to treatment based a centralized randomization scheme. The randomization code will be produced by [REDACTED]. The Parion Sciences study biostatistician, or designee, will review and approve the dummy randomization list. The final randomization list will be reviewed and approved by a designated unblinded [REDACTED] biostatistician responsible for the IDMC analyses to maintain the study blind throughout the course of the study until the final database lock.

There is no randomization in Part B. Subjects will remain in the same treatment as in

1006696
Parion Sciences Incorporated
CLEAN-PCD
SAP Version 1.0

[figure not shown]
Treatment Period 2 of Part A and will also receive open-label oral ivacaftor.

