6.2 KEY DEFINITIONS

6.2.1 Baseline

Two types of baseline will be defined for Part A. The **study baseline** is defined as the most recent nonmissing measurement (scheduled or unscheduled) collected before the first dose of study drug in the study. The definition will be applied to all demographics, background, and baseline characteristics and efficacy data analyses, including the primary endpoint analysis. The **period baseline** is defined as the most recent nonmissing measurement (scheduled or unscheduled) collected before the first dose of study drug in each Treatment Period. For Part A Treatment Period 2, the period

1006696
Parion Sciences Incorporated
CLEAN-PCD
SAP Version 1.0

baseline will be the first assessment measured after treatment-emergent (TE) period for Period 1. This definition will be applied to all safety data analyses.

For spirometry analysis in Part A, if Period 1 day 1 pre-dose data is not available, data collected at the screening visit before the test HS dose will be used as Period 1 baseline or study baseline instead of the last non-missing screening visit after the test HS dose.

For weight, height and BMI, study baseline and Period 1 baseline will be defined as the most recent non-missing measurement (scheduled or unscheduled) collected before or on the day of the first dose of study drug in Part A, Period 1. Similarly, Period 2 baseline will consider the most recent non-missing measurement (scheduled or unscheduled) collected after the TE period for Period 1 and before or on the day of first dose of study drug in Part A, Period 2.

For SGRQ and QOL-PCD, study baseline will be defined as the most recent non-missing measurement (scheduled or unscheduled) collected before or on the day of the first dose of study drug in Part A, Period 1.

For Part B, two types of baseline, study baseline and Part B baseline, will be defined. The study baseline is defined the same as study baseline for Part A. The Part B baseline is defined as the most recent non-missing measurement (scheduled or unscheduled) collected before the first dose of ivacaftor in Part B and after the last dose in Period 2.

- Change/Absolute change from study baseline in Part A and Part B will be calculated as:

post-baseline value - study baseline value.

- Change/Absolute change from period baseline in Part A will be calculated as:

post-baseline value - period baseline value.

- Change/Absolute change from Part B Baseline will be calculated as:

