8.1 PRIMARY EFFICACY ENDPOINT AND ANALYSIS

Part A

The primary efficacy endpoint for Part A is the absolute change in ppFEV1 from study baseline, after 28 days of treatment in each Treatment Period of Part A.

The null hypotheses to be tested are that the mean absolute change from study baseline in ppFEV1 after 28 days of treatment is the same for 1) VX-371 in HS versus placebo; 2) VX-371 versus placebo; 3) VX-371 in HS versus HS alone. The primary assessment of efficacy will be based on the comparison of VX-371 in HS versus HS alone.

[figure not shown]
The primary efficacy analysis is based on a mixed-effects model. This model will include the absolute change from study baseline in ppFEV1 after 28 days (Visit Day 29 for Period 1 and Day 85 for Period 2) of treatment as the dependent variable, treatment and period as fixed effects, study baseline as a covariate, and subject as a random effect. The within-subject covariance will be assumed to have the compound symmetry (CS) structure. Denominator degrees of freedom for the F-test for fixed effects will be estimated using the Kenward-Roger approximation. No imputation of missing data will be done.

The estimated mean of the dependent variable, a 95% CI, and a 2-sided p-value will be provided for each treatment. There will be no adjustment for multiplicity. Similarly, the estimated between-treatment differences along with the corresponding 95% CI and 2-sided p-values will be presented.

[figure not shown]
A sample SAS code is provided below:

1006696
Parion Sciences Incorporated
CLEAN-PCD
SAP Version 1.0

Waterfall plot of the change from study baseline in ppFEV1 at Day 29 will be plotted by treatment group.

[figure not shown]

Summary statistics for the actual values and absolute changes from study baseline in pre-dose ppFEV1 will be summarized descriptively by treatment and visit based on Part A FAS.

In addition, the actual values and absolute changes at post-HS screening from pre-HS screening visit as well as actual values and absolute changes at Day 1 post-dose from Day 1 pre-dose in each period will be summarized based on Part A Safety Set and Part B Safety Set.

1006696
Parion Sciences Incorporated
CLEAN-PCD
SAP Version 1.0

[Redacted text block consisting of multiple lines of blacked-out content]

Part B

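### As readable, SAP 8.2 Part A adjusts change in SGRQ and QOL-PCD for baseline ppFEV1 only; if the score's own baseline is left out, VX-371 in HS versus placebo loses some precision

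*SAP*

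**What the plan says.** SAP 8.1 Part A models change in ppFEV1 with "treatment and period as fixed effects, study baseline as a covariate, and subject as a random effect". The outcome there is ppFEV1, so that study baseline is ppFEV1 as well.

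SAP 8.2 Part A says SGRQ total score "will be analyzed using similar analyses as described in" Section 8.1 Part A. It treats the other endpoint likewise: "QOL-PCD Lower Respiratory Symptoms domain for each QOL-PCD questionnaire version will be analyzed" in the same manner. For each it adds: "Note that the mixed effect model will use study baseline for ppFEV1 as a baseline covariate". A redaction follows the note both times, and the sample SAS code announced in 8.1 is not readable.

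The scores have a baseline of their own. SAP 6.2.1 states: "For SGRQ and QOL-PCD, study baseline will be defined as the most recent non-missing measurement", taken on or before the day of first dosing, and both questionnaires are scheduled on Day 1. The protocol (12.3.3.1 and 12.3.3.2) names no baseline covariate. Table 2 of the SAP says only that a mixed-effects model is used.

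SAP 8.1 lists three null hypotheses, of which VX-371 in HS versus placebo is the first, and adds: "The primary assessment of efficacy will be based on the comparison of VX-371 in HS versus HS alone".

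**The concern.** When the outcome is a change score, the variable that usually explains most of its remaining spread is the baseline of that same score. Baseline ppFEV1 is a sensible covariate, since ppFEV1 severity is the stratification factor (SAP 3.6), but it can stand in for a questionnaire baseline only as far as the two are correlated.

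The design decides which comparisons this touches. Protocol 8.2.1 states that no subject switches between saline strengths. VX-371 in HS versus HS, and VX-371 versus placebo, are therefore made within subjects, and a baseline that is constant within a subject cancels. VX-371 in HS versus placebo is made between subjects, so differences in baseline score stay in its error. What is at stake is the width of that confidence interval for the two questionnaire endpoints, which carry the only secondary objective of Part A.

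**Working it through.** **The plan's own figure.** The documents give no power or precision for SGRQ or QOL-PCD. For ppFEV1, SAP 3.5.1 states about 87% power for 4 points between VX-371 in HS and placebo, with SD 7, within-subject correlation 0 and 10% dropout. Sequences 1 and 2 supply 100 subjects on VX-371 in HS and sequences 3 and 4 supply 50 on placebo, so 90 and 45 complete. SE = 7 × √(1/90 + 1/45) = 1.278. Then 4/1.278 − 1.960 = 1.17, which gives 87.9%. This agrees with the plan to within a point and confirms that the contrast's variance is the marginal variance times (1/n₁ + 1/n₂).

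**Inputs assumed, not in the documents.** Baseline SD of the score is 1 and follow-up SD is s. The baseline-to-follow-up correlation is ρ. The correlation of baseline ppFEV1 with baseline score is r in size. ppFEV1 is related to follow-up only through baseline score. The covariance is compound symmetric and both periods are observed.

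**Residual variance of the change score.**
- ppFEV1 only: 1 + s² − 2ρs − r²(1 − ρs)². With s = 1 this is 2(1 − ρ) − r²(1 − ρ)².
- Own baseline added: s²(1 − ρ²).

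The SE ratio for VX-371 in HS versus placebo is the square root of the first over the second.

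**Equal SDs (s = 1), r = 0.4.**

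| ρ | ppFEV1 only | own baseline added | SE inflation | equivalent loss of subjects |
|---|---|---|---|---|
| 0.5 | 0.960 | 0.750 | 13.1% | 22% |
| 0.7 | 0.586 | 0.510 | 7.2% | 13% |
| 0.8 | 0.394 | 0.360 | 4.6% | 8.5% |
| 0.9 | 0.198 | 0.190 | 2.2% | 4% |

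The last column is 1 minus the ratio of the two variances. Over r from 0.2 to 0.6 the inflation is 14.9% to 10.2% at ρ = 0.5 and 2.5% to 1.7% at ρ = 0.9.

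**Unequal SDs, r = 0.4.**

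| ρ | s = 1.2 | s = 0.8 |
|---|---|---|
| 0.5 | 6.0% | 27.7% |
| 0.7 | 1.5% | 22.4% |
| 0.8 | 0.1% | 21.3% |
| 0.9 | 1.0% | 24.2% |

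The equal-SD assumption matters more than r. The loss vanishes when ρs = 1, because plain change is then already the best use of baseline.

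**Checks.** A simulation with 135 subjects in about 2:2:1:1 (4,000 trials per case, REML, compound symmetry, s = 1, r = 0.4) gave inflation of 12.4%, 7.7%, 3.2% and 2.0% at the four ρ values. VX-371 in HS versus HS and VX-371 versus placebo changed by 0.0%. A separate generalised least squares calculation on the 50/50/25/25 design (r = 0.3) gave at most 0.4% for those two contrasts with 10% dropout.

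**Small questionnaire versions.** QOL-PCD is modelled per version, and some versions may be small; for example "Subjects aged 12 at Day 1 will complete the QOL-PCD-Child version themselves". With 60 subjects the simulated gain was 12.9%, 5.9%, 3.5% and 2.2%. With 12 it was 9.6%, 1.2%, 0.2% and −2.9%, the last being a small loss.

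**Single-treatment means.** SAP 8.1 also reports a P value for each treatment mean. The model treats baseline as fixed, so its SE ignores sampling variation in mean baseline. For VX-371 in HS at ρ = 0.5 with 135 subjects:
- Model variance: 0.75/90 = 0.00833, SE 0.091.
- Actual variance: 0.00833 + (1 − 0.5)²/135 = 0.01019, SE 0.101 (simulated 0.099).
- 1.96 × 0.091/0.101 ≈ 1.77, so a nominal 5% test rejects about 7.6% of the time. Simulation gave about 8%, against 5.9% with ppFEV1 only.
- At ρ = 0.9 the same steps give 0.19/90 = 0.002111 against 0.002111 + 0.01/135 = 0.002185, and about 5.4%.

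**The case against.** The strongest reply is that the premise rests on text nobody outside the sponsor can read. A redaction follows each note, the sample code is missing, and the reference to 8.1 could carry a study baseline over in the sense of the score being analysed. The note does not say that ppFEV1 is the only covariate or that it replaces another. This stands in part. A reader might infer that the plan is shown to omit the own baseline, and the documents do not prove that. But the only covariate 8.2 names is ppFEV1, and the baseline in the 8.1 model is ppFEV1 too, so omission is the natural reading.

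A second reply is that the reach is narrow: one of three listed contrasts, on secondary endpoints, in a Phase 2a trial, with an outcome that is already a change from baseline. That is correct and limits the weight of the point.

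A third is that the size depends on assumptions. That is also correct. With a follow-up SD 1.2 times the baseline SD, the loss at ρ = 0.8 is 0.1%.

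A fourth is that the change is not free, because it makes the single-treatment P values liberal when ρ is low. This stands and is counted as a cost. It does not affect the treatment differences, whose type I error was correct with either model.

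**Conclusion.** The point holds as a conditional one: if the readable text is the whole specification, VX-371 in HS versus placebo on SGRQ total and QOL-PCD Lower Respiratory Symptoms has a larger SE than it needs. The excess is about 13% to 2% for ρ from 0.5 to 0.9 under equal SDs and r = 0.4, and roughly 0% to 28% across SD ratios of 1.2 to 0.8. None of these inputs is in the documents.

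Two stronger readings should be resisted. A reader might infer that the questionnaire results would be biased; randomisation protects the contrast under either model, so only precision is lost. A reader might also infer that the comparison the SAP treats as its main one is weakened; VX-371 in HS versus HS does not change with complete pairs.

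This is a cheap improvement, not a flaw that threatens a conclusion.

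**What to change.** Unless the redacted text already does so, replace the note in SAP 8.2 Part A, for both endpoints, with: *The mixed effect model will include the study baseline of the analysed score as well as study baseline ppFEV1 as covariates.* Make the same change in the code before unblinding. Add a sentence that inference rests on the between-treatment differences and that the single-treatment P values are descriptive.

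Costs: one degree of freedom per model and no new data. There is little or no gain, and possibly a slight loss, in a very small QOL-PCD version. The single-treatment tests reject at about 8% for a nominal 5% at ρ = 0.5, and close to nominal by ρ = 0.9.

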8.5 SUMMARY OF EFFICACY ANALYSES

Table 2 below shows a brief summary of the efficacy analyses aforementioned in Section 8.

[figure not shown]
Table 2. Summary of efficacy analysis

Part A:

Name	Endpoint	Analyses
Primary efficacy endpoint and analysis	Absolute change in ppFEV1 from study baseline at Day 29 within each treatment Period	
 - Mixed-effects model - Waterfall plot - [REDACTED]
Secondary efficacy endpoint and analysis - SGRQ	Change in SGRQ total score from study baseline, after 28 days of treatment in Part A	For SGRQ total score: 
 - Mixed-effects model - Waterfall plot - Descriptive analysis - [REDACTED]
Secondary efficacy endpoint and analysis - QOL-PCD	Change in QOL-PCD Lower Respiratory Symptoms domain score from study baseline, after 28 days of treatment in Part A	For QOL-PCD Lower Respiratory Symptoms domain: 
 - Mixed-effects model - Waterfall plot - Descriptive analysis - [REDACTED]

1006696
Parion Sciences Incorporated
CLEAN-PCD
SAP Version 1.0

Part B:

Name	Endpoint	Analyses
Primary efficacy endpoint and analysis	Absolute change in ppFEV1 from study baseline and Part B baseline at Day 29	
- ANCOVA model- Waterfall plot- Descriptive analysis
Secondary efficacy endpoint and analysis - SGRQ	Change in SGRQ total score from study baseline and Part B baseline, after 28 days of treatment in Part B	For SGRQ total score: 
- ANCOVA model- Waterfall plot- Descriptive analysis

1006696
Parion Sciences Incorporated
CLEAN-PCD
SAP Version 1.0

Secondary efficacy endpoint and analysis - QOL-PCD	Change in QOL-PCD Lower Respiratory Symptoms domain score from study baseline and Part B baseline, after 28 days of treatment in Part B	For QOL-PCD Lower Respiratory Symptoms domain: 
- ANCOVA model- Waterfall plot- Descriptive analysis
A large solid black rectangular redaction box covering the entire body of the table.		

1006696
Parion Sciences Incorporated
CLEAN-PCD
SAP Version 1.0

[Redacted]

[Redacted]

[figure not shown]
[Redacted]

[Redacted]

[Redacted]

1006696
Parion Sciences Incorporated
CLEAN-PCD
SAP Version 1.0

10 SAFETY

All safety analyses will be based on the set of data associated with the treatment emergent period for Part A Treatment Period 1, the treatment emergent period for Part A Treatment Period 2, and the treatment emergent period for Part B. Part A safety analyses will be based on the Part A Safety Set. The summaries will be by treatment received in Part A. Part B safety analyses will be based on the Part B Safety Set. The summaries will be provided by treatment received in Part B. For subjects receiving study drug from more than one treatment group in the same treatment period for Part A, the treatment group allocation will be determined using the following order: VX-371 + HS > VX-371 + Placebo > HS > Placebo.

For safety analysis, the period baselines will be used for Part A and the Part B baseline will be used for Part B. The overall safety profile of study drug will be assessed in terms of the following safety and tolerability endpoints:

- Treatment-emergent adverse event (TEAEs)
- Clinical laboratory values (i.e., urine, serum and plasma chemistry, and hematology)
- ECG results
- Spirometry
- Vital signs
- Pulse oximetry

10.1 ADVERSE EVENTS

[figure not shown]
For analysis purposes, AEs will be classified as pre-treatment adverse events (AEs) or TEAEs, defined as follows:

Pre-treatment AEs are defined as any AEs that started before the initial dosing of study drug.

TEAE: any AE that increased in severity or that was newly developed during the treatment emergent period for Part A Treatment Period 1 or Part A Treatment Period 2 or Part B. An AE that starts (or increases in severity) during a specific Part A Treatment Period or Part B will be attributed to the study drug the subject was receiving during the corresponding Part A Treatment Period or Part B.

1006696
Parion Sciences Incorporated
CLEAN-PCD
SAP Version 1.0

For AEs with missing or partial start date, if there is no clear evidence that the AEs started (or increased in severity) before the first dose of Part A, the start date will be imputed to the first dosing date of Part A and the AE assigned to the treatment in Part A Treatment Period 1. For AEs with missing or partial start date, if there is no clear evidence that the AEs started (or increased in severity) before the first dose of Part B, the start date will be imputed to the first dosing date of Part B and the AE assigned to the treatment in Part B.

For the cases in which the end of treatment emergent Period 2 is on the same day as the start of treatment emergent Period for Part B, any AE starting on the same day as start of treatment emergent Period for Part B, will be assigned to the treatment in Part B.

AE summary tables for Part A and B will be presented for TEAEs only and will include the following:

[figure not shown]
- All TEAEs
- TEAEs by worst/highest relationship (includes Related, Possibly Related, Unlikely Related and Not Related)
- TEAEs by maximum severity (includes Mild, Moderate, Severe, and Life threatening)
- TEAEs leading to treatment discontinuation
- TEAEs leading to drug interruption
- Serious TEAEs
- TEAEs leading to death
- Frequently reported TEAEs

A frequently reported TEAE is defined as more than 2 subjects who have TEAE preferred term incidence for at least 1 treatment group.

Summaries will be presented by treatment and by MedDRA (version 18.1) system organ class (SOC) and preferred term using frequency counts and percentages (i.e., number and percentage of subjects with an event). When summarizing the number and percentage of subjects with an event, subjects with multiple occurrences of the same AE or a continuing AE will be counted once, only the maximum severity level will be presented in the severity summaries, and the worst/highest relationship level in the

1006696
Parion Sciences Incorporated
CLEAN-PCD
SAP Version 1.0

relationship summaries. An AE overview table will be provided for the following categories:

- TEAEs
- Related TEAEs (includes Related and Possibly Related)
- Serious TEAEs
- Related Serious TEAEs
- TEAEs Leading to Study Drug Interruption
- TEAEs Leading to Study Drug Discontinuation
- TEAEs with Outcome of Death

In addition, a listing containing individual subject AE data for all deaths and other serious AEs will be provided separately for Part A and Part B. All AEs, including pre-treatment AEs, will be presented in individual subject data listings.

TEAEs related to study device will also be summarized by system organ class and preferred term using frequency counts and percentages (i.e., number and percentage of subjects with an event).

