**8.1.3.1.2 Washout Period**

Subjects will undergo a Washout Period of 28 days (+ 3 days) between Treatment Period 1 and Treatment Period 2. Subjects should continue to maintain a consistent medication and airway clearance regimen throughout the Washout Period. The Washout Period may be extended for an additional 28 days for acute upper or lower respiratory infections following discussion and approval of the Parion medical monitor.

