6.2.2 Treatment Emergent Period

Treatment-emergent (TE) period for Part A Treatment Period 1:

1006696
Parion Sciences Incorporated
CLEAN-PCD
SAP Version 1.0

- The Treatment-Emergent Period will correspond to the interval from the first dose date of Treatment Period 1 to 28 days after the last dose date of Treatment Period 1 or the date before the first dose date of Treatment Period 2 or the safety follow-up visit, whichever occurs earlier.

TE period for Part A Treatment Period 2:

- The treatment emergent period will correspond to the interval from the first dose date of Treatment Period 2 to 28 days after the last dose date of Treatment Period 2 or the date before the first dose date of Part B or the safety follow-up visit, whichever occurs earlier.

Treatment-Emergent Period for Part B:

- The treatment emergent period will correspond to the interval from the first dose date of study drug in Part B to 28 days after the last dose date of Part B or the safety follow-up visit, whichever occurs earlier.

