6.3 MISSING DATA

Imputations for missing or partially missing start/end dates for prior/concomitant medications and adverse events are described in [Appendix V](#).

Imputation for missing individual QOL-PCD scores is described in [Appendix II](#).

[figure not shown]
No other imputations will be performed for missing data. Observed data will be used in the analyses.

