APPENDIX V HANDLING MISSING DATE

Prior/Concomitant medication:

Missing or partial medication start date:

- If only day is missing, use the first day of the month.
- If day and month are both missing, use the first day of the year.
- If day, month and year are all missing, use a date before the first dose date (in practice, use Jan. 01, 2000 to impute).

Missing or partial medication stop date:

- If only day is missing, use the last day of the month.
- If day and month are both missing, use the last day of the year.
- If day, month and year are all missing, assign 'continuing' status to stop date (in practice, use Dec. 31, 2050 to impute).

Adverse Event:

Imputation of missing AE start date:

- If AE start date is completely missing and AE end date is after the first dose date in Part A Period 1 but before first dose date in Part B, then use the first dose date in Part A Period 1 as the AE start date and classify the AE as a TEAE; if the AE end date is after the first dose date in Part B then
 - 1) Use the first dose date in Part A Period 1 as the AE start date
 - 2) Use the first dose date in Part B as the AE start date.
- If AE start date is completely missing, and AE end date is before the first dose date in Part A Period 1, then the AE is not a TEAE.
- If both AE start date and AE end date are completely missing then
 - 1) Use the first dose date as AE start date in Part A Period 1 and classify the AE as a TEAE for Part A
 - 2) Use the first dose date as AE start date in Part B and classify the AE as a TEAE for Part B

1006696
Parion Sciences Incorporated
CLEAN-PCD
SAP Version 1.0

Statistical Analysis Plan

- If only day is missing, use the first day of the month or the first dose date whichever is later, unless the AE start month is before the first dose date in which case, the AE start date remains missing and this AE is not a TEAE.
- If day and month are both missing, use the first day of the year or the first dose date whichever is later, unless the AE start year is before the first dose date. In this case, the AE start date remains missing and this AE is not a TEAE.

Imputed AE start date must be earlier than the original AE end date, otherwise set imputed start date = original AE end date and the AE is not a TEAE.

Missing AE causality

For summary tables of related AEs, report missing causality as 'related'.

Missing AE Severity

[figure not shown]
There will be no imputation of missing AE severity.

Missing SAE category

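### SAP 10.1 charges AEs with partial start dates to the Period 1 treatment even when the recorded month rules Period 1 out, and Appendix V's end-date test drops a few AEs that can only have begun on treatment

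*SAP*

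**What the plan says.** SAP 10.1 first gives a principle: an AE that starts or worsens in a period "will be attributed to the study drug the subject was receiving during the corresponding Part A Treatment Period or Part B". It then gives a default for missing or partial start dates. Unless onset was clearly before the first Part A dose, the start is "imputed to the first dosing date of Part A and the AE assigned to the treatment in Part A Treatment Period 1". A parallel sentence covers Part B: unless onset was clearly before the first Part B dose, the start is "imputed to the first dosing date of Part B and the AE assigned to the treatment in Part B". No sentence sends a partial-date AE to Period 2.

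SAP 6.3 points elsewhere: "Imputations for missing or partially missing start/end dates for prior/concomitant medications and adverse events are described in" Appendix V. For AEs, Appendix V keeps the known part of the date: "If only day is missing, use the first day of the month or the first dose date whichever is later", and likewise the first day of the year when only the year is known. It does not say which first dose date is meant for partial dates. It adds an end-date test: "Imputed AE start date must be earlier than the original AE end date, otherwise set imputed start date = original AE end date and" the AE then does not count as a TEAE.

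SAP 6.2.2 ends the Period 1 treatment-emergent period at the earliest of three limits. One runs "to 28 days after the last dose date of Treatment Period 1"; the others are the day before the first Period 2 dose and the safety follow-up.

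Protocol 12.3.4.1 has the same Period 1 default. It accepts that a partial-date AE may count in both Period 1 and Part B, but assigns the Part B-imputed AE to the Period 1 treatment, where the SAP assigns it to Part B. SAP Section 11 lists no changes from the protocol.

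**The concern.** Defaulting to the first dose is cautious when the question is only whether an AE is treatment-emergent. In a crossover the same default also decides which treatment is charged. In sequences 1 and 3 a later control-period event would go to the VX-371 treatment; in sequences 2 and 4 a later VX-371 event would go to the control. A recorded month lying wholly in Period 2 or Part B is no evidence of onset before Part A, so 10.1's condition is met and the default applies.

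AE results are part of the primary endpoint in both parts, the AE summary tables show TEAEs only, and they are presented by treatment. A programmer working from 10.1 and one working from Appendix V would produce different tables. The end-date test has a separate effect: when imputed start and end coincide, an AE leaves every AE summary table even if it can only have begun on treatment.

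**Working it through.** The documents give no figure on this point, so the rules are applied as written.

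**Worked example.** First dose 5 March; + 56 days = 30 April (Day 57, Period 2); + 84 = 28 May (Day 85, Part B); + 112 = 25 June (Day 113). The Period 1 treatment-emergent period ends by 29 April. Appendix V is read here with the first dose date as Day 1.

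| Recorded | Possible onset | SAP 10.1 | Appendix V |
|---|---|---|---|
| Start May, end 20 May | Period 2 only | Period 1 drug | 1 May, Period 2 |
| Start June | Part B only | Period 1 drug, and also Part B | 1 June, Part B |
| Start May, end 1 May | 1 May only (Period 2 Day 2) | Period 1 drug | not a TEAE |

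**How often the month excludes Period 1.** Assumptions: only the onset month is known; onset and first-dose dates are spread evenly over a four-year calendar cycle; Period 2 starts on Day 57 and Part B on Day 85.

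For onset on Day 56 + k, the month excludes Days 1 to 56 exactly when the day of the month is k or less. Day numbers 1 to 28 each occur 12 times a year, so for k up to 28 the share is 12k/365.25.

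- *Onset Day 57 to 84* (k = 1 to 28, mean 14.5): 12 × 14.5 / 365.25 = 47.64% exclude Period 1; 52.36% do not. Section 10.1 charges 100% to the Period 1 drug.
- *Onset Day 57 to 112, no Part B* (k = 1 to 56): the 29th, 30th and 31st occur 11.25, 11 and 7 times a year. The sum is 12 × 406 + 347.25 + 358.25 + 26 × 365.25 = 15,074. Divided by 56 × 365.25 = 20,454, this is 73.70%; 26.30% do not exclude Period 1.
- *Onset Day 85 to 112, Part B entered*: the month still reaches Period 1 only on Day 85 (30th or 31st, 18 a year) or Day 86 (31st, 7 a year): 25 / (28 × 365.25) = 0.24%. It lies wholly in Day 85 or later for 47.64%, by the first calculation shifted by 28 days. The remaining 52.12% reach Period 2 but not Period 1. Section 10.1 counts 100% in Part B and 100% under the Period 1 drug as well.

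**Deferring to Appendix V alone.** If its first dose date means Day 1, the imputed start falls before Day 85 for 100 − 47.64 = 52.36% of true Day 85 to 112 onsets, which would then leave Part B.

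**End-date test.** Certain losses are AEs dated by month only, in a month after the first-dose month, that end on the 1st. For one-day AEs this is 12/365.25 = 3.3%. A one-year grid of first-dose dates with onset on Days 1 to 140 (365 × 140 = 51,100 cases) gives 1,668 certain losses (3.3%) for one-day AEs, and none for AEs lasting 3 or 7 days.

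**Effect on a comparison (illustration).** Let a fraction f of Period 2 AEs have partial dates, with 50 subjects in each of sequences 1 and 2 and event rates per subject and period that differ by Δ between VX-371 in HS and HS alone. Under 10.1 the expected difference in event counts is 50Δ + 50Δ(1 − 2f) = 100Δ(1 − f). With Δ = 0.10, a difference of 10 events becomes 9.5 at f = 5% and 9.0 at f = 10%. Part B events that are also charged to Period 1 are left out.

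**The case against.** - *SAP 6.3 already names Appendix V, so misattribution arises only if 10.1 is programmed.* True: this is a conflict between two sections, and the outcome depends on which is followed. But 10.1 is the section that governs the AE tables, and Appendix V cannot settle the matter while its first dose date is undefined for partial dates.
- *The default is protocol text, and the protocol accepts double counting.* This stands for the Part B sentence, which should stay. Protocol 12.3.4.1 does not address a recorded month that excludes Period 1.
- *There is no base rate.* This stands in full. Every percentage above is conditional on the start day being missing. Protocol 13.1.1.3 requires the date of first occurrence and Protocol 13.3 requires missing data to be queried, so such AEs should be uncommon. The tables count subjects, so a moved event changes a cell only if that subject lacks the same term under that treatment.
- *A shorter fix would do: let Appendix V govern.* If its first dose date were read separately for each part, as its bullets for completely missing dates suggest, the 52.4% loss from Part B would not arise. The text does not say so, and it has to.
- *Allowing equal dates also turns AEs that end on the first-dose date, with possible earlier onset that month, into TEAEs.* This is a real side effect: in the one-year grid, 2,033 − 1,668 = 365 of the one-day cases (0.7%) end on the first-dose date. It matches 10.1's default of treating an AE as treatment-emergent unless it clearly began earlier.

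**Conclusion.** The concern holds on both counts. As written, 10.1 charges to the Period 1 treatment AEs whose recorded month or year shows that they began later, against its own principle and against Appendix V. The recorded month would correct 47.6% of day-missing Period 2 onsets in subjects who enter Part B, and 73.7% in those who do not. The end-date test is a boundary error with provable effect only on one-day AEs on the first of a month. For completely missing start dates the two sections broadly agree.

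The shares rest on evenly spread dates and the nominal schedule; the number of events affected cannot be derived from the documents and is probably small. Efficacy analyses are untouched. This is a minor point, worth correcting because it moves events between the treatments being compared on a primary safety endpoint.

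**What to change.** 1. In SAP 10.1, apply the Period 1 default only when the known parts of the start date and the end date allow onset in the Period 1 treatment-emergent period of SAP 6.2.2. If they exclude it, assign the AE to the Period 2 treatment when onset in the Period 2 treatment-emergent period is possible. Keep the separate Part B sentence. True Day 85 to 112 onsets then stay 100% in Part B; in Part A, 0.2% fall under Period 1, 52.1% under Period 2 and 47.6% are not counted.
2. In Appendix V, state which first dose date applies to partial dates and that Appendix V and 10.1 agree. Require the imputed start to be no later than the end date. Decide TEAE status by whether any onset date compatible with the recorded information falls in a treatment-emergent period. This matters because Protocol 8.1.3.1.2 says "The Washout Period may be extended for an additional 28 days" for acute respiratory infection; washout days more than 28 days after the last Period 1 dose belong to no treatment-emergent period.
3. In SAP Section 11, record the departures from Protocol 12.3.4.1, including the existing change in Part B assignment.

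The cost is a few SAP sentences, one Section 11 entry and a few programming lines. Limits remain: AEs whose month straddles the start of Period 2 still default to Period 1 (52.4%, or 26.3% without Part B). Up to 52.4% of day-missing AEs truly starting on Days 57 to 84 also stay counted in Part B, as 10.1 already does, unless the end date rules it out.
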